6.2.2 Analysis of Secondary Efficacy Variables

6.2.2.1 Secondary Efficacy Variables: Primary Analysis

Secondary efficacy variables are the following:

- Total (first and recurrent) HF events
- Improvement in NYHA class from Baseline to Month 12
- Change from baseline to Month 6, 9 and 12 in TSS of the KCCQ

- Time to first occurrence of composite renal endpoint: sustained decrease in eGFR $\geq 50\%$ relative to baseline over at least 4 weeks, or sustained eGFR decline $< 15 \text{ ml/min}/1.73 \text{ m}^2$ or initiation of dialysis or renal transplantation
- Time to ACM

See Section 4.7 for details regarding the testing hierarchy for secondary endpoints and nominal significance levels.

Total HF events will be analyzed in a similar fashion to the primary endpoint, using an LWYY model including treatment group as fixed effect and including pooled region for stratified analyses and baseline LVEF ($< 60\%$, $\geq 60\%$) as stratification factors. A treatment policy strategy will be applied for treatment discontinuation, i.e., all events and follow-up time will be included in the analysis; all-cause death will be a censoring event for a while-alive approach.

The percentage of participants with improvement in NYHA class from Baseline to Month 12 will be analyzed with a logistic regression model including factors for treatment group and stratification levels. A patient is considered as having improved in NYHA class, if the NYHA class at Month 12 (Visit 6) is at least one category improved compared to the baseline visit. A composite strategy will be applied to those cases, where no measurement at Visit 6 is available due to stop of treatment prior to Visit 6. That means these patients are considered to have not improved in NYHA class. Participants who are still in the treatment period at Visit 6, but have NYHA assessment missing, will be imputed by taking the mean of the last available measurement prior to Visit 6 and the first measurement thereafter. Participants with no further value available after Visit 6 or whose only available information is from EoS visit will be imputed as non-responders. Participants with missing baseline value will be excluded from the analysis. Odds ratio and two-sided 95% confidence intervals will be provided for the comparison of finerenone vs. placebo treatment group. In addition, change from baseline in NYHA class will be summarized descriptively using shift tables, presented by visit and any time post-baseline. These tables will present the number of participants with the class at a certain visit by their respective baseline class.

The absolute change from baseline including measurements up to Month 12 of the KCCQ TSS will be analyzed by a repeated measures mixed model including the factors treatment group, baseline, visit, baseline-by-visit interaction, and factors for the stratification levels. For each treatment group a separate covariance pattern will be estimated based on an unstructured covariance to adjust for within participant variance.

In case the model does not converge, different covariance patterns will be used, in the following order, until convergence is met: separate unstructured covariance patterns, separate Toeplitz covariance patterns, separate Autoregressive(1) covariance patterns, and finally separate Compound Symmetry covariance patterns will be used.

Differences between the finerenone and the placebo treatment groups will be calculated with two-sided 95% CIs. The comparison assumes a common treatment effect across Month 6, 9 and 12 and will be considered primary. This analysis will investigate the effect on the KCCQ TSS while patients are alive and irrespective of any permanent treatment discontinuation. This means that all observed values will be included in the analysis.

The primary analysis of the secondary time-to first event variables (i.e. composite renal endpoint and ACM) will be done with a stratified log-rank test for testing and a stratified Cox proportional hazards model for obtaining a point estimate with 95% CIs. The Cox proportional hazards model will be stratified according to the stratification factors and include

treatment group as fixed effect. For the composite renal endpoint, the cause-specific point estimate with 95% confidence interval for the censoring event of death will also be presented. Cumulative incidence function plots and summaries (calculated using Aalen-Johansen estimates) will be produced for the composite renal endpoint and the censoring event of death. In addition, components of the composite renal endpoint will be analyzed. Furthermore, Aalen-Johansen plots will be displayed for the ACM endpoint.

Only central laboratory measurements before initiation of dialysis or renal transplantation will be considered for the definition of the individual eGFR-based components of the renal endpoint. At the up-titration, restart and safety check visits, only a local laboratory measurement is obtained. These values will be checked for a potential eGFR event and, in case of decline, the investigators will be advised to retest eGFR centrally in an unscheduled visit; determination of an eGFR event will then be based on this value. If an initial decrease in eGFR occurs on the EoS visit, there will be another confirmatory measurement taken at least 4 weeks later to confirm the initial decrease. The individual components “Sustained decrease of eGFR $\geq 50\%$ from baseline over at least 4 weeks” as well as “Sustained eGFR decline $<15\text{ml/min}/1.73\text{m}^2$ ” will be programmatically derived. Only in the event that the eGFR decrease was confirmed by at least one additional eGFR measurement taken at least 4 weeks later, it will be considered as a sustained decrease and counted for the renal endpoint. The confirmatory additional eGFR measurements will typically be taken during an unscheduled visit. The date used for the analysis will be the date of the initial sample exceeding the threshold. If there was no confirmatory assessment, events will only be counted for the renal endpoint when the patient died after the initial decrease or the patient went on renal replacement therapy such as dialysis or transplantation prior to their scheduled confirmatory assessment. If there is an intermediate measurement that does not confirm the initial decrease, the event will not be counted for the renal endpoint.

eGFR events will be counted from the day of randomization until the EoS visit (or EoS notification + 28 days if EoS visit is missing). Participants will be censored at the earliest of the date of their last visit when a central eGFR measurement is available or EoS visit date (or EoS notification + 28 days if EoS visit is missing). If no post-baseline eGFR measurement is available, participants will be censored at day 1 (randomization date).

The other two components of the renal composite endpoint, i.e. initiation of dialysis or renal transplantation, will be adjudicated. To account for events of initiation of dialysis or renal transplantation after the last eGFR is recorded at a clinic visit, such events will be included in the efficacy analysis of the composite renal endpoint if they occur in the period up to the next planned clinic visit (+ 1 month) or EoS visit date (or EoS notification + 28 days if EoS visit is missing) or death date or last contact date. If no post-baseline eGFR measurement is available, the next planned visit is the date of Visit 2 (Month 1). Censoring will be applied at the last eGFR date (or day 1 if last eGFR date is missing) or at the earliest of EoS visit date (or EoS notification + 28 days if EoS visit is missing) or death date or last contact date, if these occur earlier than the next eGFR date + 1 month.

Randomized participants without an event of the composite renal endpoint at the time of analysis will be censored at the latest censoring date of their individual components.

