Only adjudicated outcome events will be used for analysis of the primary and secondary efficacy variables (except for sustained decrease in eGFR $\geq 50\%$ relative to baseline over at least 4 weeks and sustained eGFR decline $< 15 \text{ ml/min}/1.73\text{m}^2$ which will be derived from central laboratory measurements and not be adjudicated); Section 6.2.4 specifies how investigator-reported outcomes for these variables will be summarized. Outcome events for exploratory efficacy variables (e.g. non-fatal myocardial infarction, non-fatal stroke, etc.) will not be adjudicated.

The stratified analyses mentioned in this SAP will be conducted in consideration of the randomization stratification factors:

- LVEF: $< 60\%$, $\geq 60\%$
- Pooled region for stratified analyses: randomization will be stratified by country/region, for the analyses individual countries/regions will be combined into pooled regions as follows:
 - Western Europe and Oceania: Australia, Austria, Denmark, Germany, Israel*, Netherlands, New Zealand, United Kingdom
 - Southwestern Europe: Italy, Portugal, Spain
 - Central Europe: Czechia, Hungary, Poland, Slovakia
 - Southeastern Europe: Bulgaria, Greece, Romania, Turkey
 - Northeastern Europe: Finland, Latvia, Lithuania, Russia, Ukraine
 - Asia: China, Hong Kong, India, Japan, Malaysia, South Korea, Taiwan
 - North America: Canada, United States of America
 - Latin America: Argentina, Brazil, Colombia, Mexico

*Although not geographically located in Western Europe or Oceania, Israel has been included in this pooled region.

In case of issues (e.g. model convergence) with using these predefined pooled regions at the final analyses, the pooled regions may be further combined. Any such changes will be described in the CSR.

All participants will be analyzed according to their correct stratification category. In case of a large number of stratification errors ($\geq 5\%$ of all patients in the FAS), the primary analysis will also be repeated based on the stratification category used in the randomization as a sensitivity analysis.

In case a death cannot be clearly adjudicated as CV-related or non-CV related, it will be adjudicated as undetermined death. Undetermined deaths will be handled as non-CV deaths for the analysis, unless otherwise specified. Where applicable, the combined results of non-CV deaths and undetermined death will be displayed along with results for the individual categories.

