4.5.6 Subgroup Analyses

Exploratory subgroup analysis will be done for the primary and secondary efficacy variables. The subgroup analyses will include subgroups based on the stratification factors. The list of key subgroups (in addition to the stratification factors) and other subgroups analyzed is specified below. Analysis will include descriptive statistics, graphical display of estimated treatment effects with 95% confidence intervals (CIs) in a forest plot and a statistical test for interaction.

Subgroups based on stratification factors

- Pooled region for subgroup analysis (Western Europe, Oceania and Others; Eastern Europe; Asia; North America; Latin America); the subgroup Western Europe, Oceania and Others combines the groups Western Europe and Oceania and Southwestern Europe from the pooled region for stratified analyses. The subgroup Eastern Europe combines the groups Central Europe, Southeastern Europe, and Northeastern Europe from the pooled region for stratified analyses.
- LVEF (<60%, \geq 60%)

Key subgroups

- Baseline serum potassium value (\leq 4.5, $>$ 4.5 mmol/L)
- eGFR category at baseline (eGFR $<$ 60, \geq 60 mL/min/1.73 m²)
- Atrial fibrillation at baseline electrocardiogram (ECG) (present, absent)
- Diabetes Mellitus at baseline (present, absent)
- Index HF event (very recent (\leq 7 days before randomization), recent ($>$ 7 days – \leq 3 months), $>$ 3 months or no index HF event).

Other subgroups

- Race (white, black, Asian, other)
- Sex (male, female)
- Age (\leq median vs. $>$ median)
- Baseline body mass index (BMI) ($<$ 30 vs. \geq 30 kg/m²)

- Systolic blood pressure (SBP) at baseline (\leq median vs. $>$ median)
- Angiotensin-converting enzyme inhibitor (ACEI), angiotensin receptor blocker (ARB) or angiotensin receptor-neprilysin inhibitor (ARNI) use at baseline (yes, no)
- Treatment with sodium-glucose transport proteins-2 inhibitor (SGLT-2i) (yes, no)
- NYHA functional class at baseline (II, III/IV)
- Baseline NT-proBNP (\leq median vs. $>$ median)
- Baseline UACR (<30 vs. ≥ 30 mg/g)

For subgroups split by median, the FAS will be taken as reference population for derivation of median.

Individual country analyses, e.g. for Japan, required for regulatory purposes, will be included in a country-specific study SAP.

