A responder analysis for the KCCQ TSS will also be performed, defining patients with an increase of ≥ 5 points from baseline to Month 12 (or, for those with a baseline score of >95 , a score of >95 at Month 12 without decline from baseline) as a responder. All observed values will be included irrespective of any permanent treatment discontinuation. In case of missing data, a patient’s last available post-baseline score prior to Month 12 will be used (i.e. while-alive strategy) unless the patient died before Month 12 in which case they will be imputed as a non-responder (i.e. composite strategy). Responder status will be analysed using a logistic regression model including treatment, baseline TSS and stratification factors as covariates; the odds ratio and associated 95% CI will be reported. This analysis will be repeated for cut-offs of ≥ 10 points increase from baseline to Month 12 (or maintaining a score of >90 from baseline to Month 12 without decrease from baseline) and ≥ 20 points increase (or maintaining a score of >80 without decrease from baseline). These cut-offs correspond to small (≥ 5), moderate (≥ 10) and large (≥ 20) clinically meaningful improvements (Spertus et al, 2005). A

further analysis will define those responders who do not experience a ≥ 5 points decrease from baseline (or, for those with a baseline score of <5 , a score of ≥ 5 at Month 12). This is equivalent to not experiencing a small deterioration. The number and percentage of patients who are responders or non-responders per each of the above criteria will be presented at Months 6, 9 and 12. This will include a breakdown of the criteria met for response (e.g. increase from baseline of ≥ 5 , >95 at baseline and post-baseline visit) or non-response (e.g. change from baseline of <5 , >95 at baseline and ≤ 95 at post-baseline visit, missing score at post-baseline visit).

A second responder analysis for the KCCQ TSS will use the thresholds derived from the anchor-based analyses with the Patient Global Impression of Severity (PGIS) and Patient Global Impression of Change (PGIC) for a clinically meaningful within-patient change in KCCQ TSS at month 6, 9 and 12, respectively, which have been performed separately on blinded data (cf. Section 6.2.3.1). The derived thresholds are

- Minimally important within-patient improvement: 9.09
- Moderate within-patient improvement: 19.85

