These thresholds will be used for each timepoint.. All observed values will be included irrespective of any permanent treatment discontinuation. In case of missing data, a patient's last available post-baseline score prior to Month 6, 9 or 12, respectively, will be used unless the patient died before the respective scheduled visit in which case they will be imputed as a non-responder. Responder status will be analysed using a logistic regression model at each timepoint including treatment, baseline TSS and stratification factors as covariates; the odds ratio and associated 95% CI will be reported.

Empirical cumulative density functions will be plotted for Months 6, 9 and 12, with change from baseline in KCCQ TSS (+100 to -100, ordered from greatest possible improvement to greatest possible worsening) on the x-axis and proportion of participants achieving this change or greater on the y-axis. Separate curves will be presented for each treatment group.

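### The confirmatory logistic model for NYHA improvement omits baseline NYHA class; adding it is an optional, low-cost gain in efficiency that is nil to small in most scenarios

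*SAP*

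**What the plan says.** SAP 6.2.2.1 and protocol 9.4.1.2 specify the same model: the percentage improved "will be analyzed with a logistic regression model including factors for treatment group and stratification levels". A participant counts as improved if the Month 12 class is at least one category better than that participant's own baseline class. SAP 4.1 limits the stratification factors to LVEF (two levels) and pooled region (eight levels): "The stratified analyses mentioned in this SAP will be conducted in consideration of the randomization stratification factors".

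Other models in the SAP do adjust for the baseline value of their outcome:

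- KCCQ TSS, in the same testing step as NYHA (SAP 6.2.2.1): "repeated measures mixed model including the factors treatment group, baseline, visit, baseline-by-visit interaction, and factors for the stratification levels".
- First KCCQ responder analysis (SAP 6.2.2.3): "logistic regression model including treatment, baseline TSS and stratification factors as covariates".
- Second KCCQ responder analysis (SAP 6.2.2.3): "logistic regression model at each timepoint including treatment, baseline TSS and stratification factors as covariates".

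Baseline NYHA class is used only in the baseline table (SAP 6.1.2), the shift tables (SAP 6.2.2.1) and an exploratory subgroup split as II vs III/IV with an interaction test (SAP 4.5.6).

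Under SAP 4.7, if the trial runs to its end, NYHA and KCCQ are tested by Bonferroni-Holm at 0.04967/2, with the second of the two at 0.04967. The renal endpoint is formally tested only if both are rejected.

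**The concern.** An outcome defined relative to a starting class will often depend on that class. If it does, leaving class out of a logistic model moves the treatment odds ratio toward 1 and lowers the power of the treatment test. The test stays valid, because randomization protects it.

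What is at stake is efficiency in a confirmatory test that also stands in front of the renal endpoint. The shift tables and the subgroup analysis describe results by class but do not change the power of that test. The KCCQ responder models show that the SAP adjusts binary improvement outcomes for baseline elsewhere, and it gives no reason for treating NYHA differently.

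**Working it through.** **The plan's own figure.** With interim and final statistics bivariate normal, correlation √(2/3), and an interim two-sided boundary of 0.0027, the final level giving 0.05 overall is 0.049674. This matches the stated 0.04967. The first Holm step is 0.04967/2 = 0.024835, critical value 2.244. The documents state no power for NYHA.

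**Inputs.** From the SAP: N = 6000 and 1:1 allocation (section 3), so n = 3000 per arm, and the levels above (4.7). Assumed: 70% class II, placebo improvement rates in class II / III–IV, and a common within-class odds ratio (OR). Region and LVEF are left out at first.

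**Formulas.** For class k with share m_k, placebo rate p0k and finerenone rate p1k, where odds(p1k) = OR × odds(p0k):

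- Current model: P_j = Σ m_k p_jk; b = logit P1 − logit P0; SE² = 1/[nP0(1−P0)] + 1/[nP1(1−P1)].
- With class: w_jk = n m_k p_jk(1−p_jk); information I = Σ w0k w1k/(w0k + w1k); SE = 1/√I; b = ln OR.
- Power = Φ(b/SE − 2.244).

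**Worked case, 10%/35%, OR 1.2.** The finerenone rates are 11.76% and 39.25%.

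- Current model: P0 = 0.7×0.10 + 0.3×0.35 = 0.1750. P1 = 0.7×0.1176 + 0.3×0.3925 = 0.2001. b = ln 1.179 = 0.1650, SE = 0.0663, z = 2.490, power 59.7%.
- With class: w0 = 189.0 and 204.8; w1 = 218.0 and 214.6. I = 101.2 + 104.8 = 206.0, SE = 0.0697. b = ln 1.2 = 0.1823, z = 2.617, power 64.5%.
- Gain 4.8 points; relative efficiency (2.617/2.490)² = 1.105.

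**Gain in power (points) for OR 1.1 / 1.2 / 1.3 / 1.4, 70% class II.** The last column assumes that 10% of class II and 25% of class III–IV count as not improved for lack of a Visit 6 value.

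| Placebo rates II / III–IV | At 0.04967/2 | At 0.04967 | At 0.04967/2, with non-response |
|---|---|---|---|
| 15%/25% | 0.3 / 0.7 / 0.3 / 0.0 | 0.4 / 0.6 / 0.2 / 0.0 | 0.1 / 0.2 / 0.1 / 0.0 |
| 15%/30% | 0.7 / 1.5 / 0.5 / 0.0 | 0.8 / 1.3 / 0.3 / 0.0 | 0.2 / 0.6 / 0.4 / 0.1 |
| 10%/35% | 1.7 / 4.8 / 2.6 / 0.4 | 2.1 / 4.3 / 1.6 / 0.2 | 0.7 / 2.5 / 2.1 / 0.6 |
| 10%/45% | 3.0 / 8.6 / 4.7 / 0.8 | 3.7 / 7.6 / 3.0 / 0.4 | 1.3 / 4.5 / 4.0 / 1.3 |

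With equal rates (18%/18%) and no non-response, the gain is 0 throughout. At 10%/35%, half alpha, the gains are 2.0 / 4.7 / 1.6 / 0.1 with 50% class II and 1.3 / 4.0 / 2.6 / 0.5 with 80%.

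**Simulation with eight regions and LVEF in both models** (4000 paired runs per scenario, half alpha, class II share 52% to 92% across regions, standard error at most 0.6 points):

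| Placebo rates II / III–IV | No non-response | With 10%/25% non-response |
|---|---|---|
| 15%/30% | 0.5 / 1.1 / 0.4 / 0.0 | 0.5 / 0.5 / 0.5 / 0.1 |
| 10%/35% | 2.2 / 4.4 / 2.2 / 0.3 | 0.8 / 2.1 / 2.5 / 0.6 |
| 10%/45% | 3.1 / 7.4 / 4.3 / 0.7 | 1.1 / 3.5 / 3.9 / 1.4 |

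**Different parametrization.** With the effect set so that the current model has 80% power, over class II shares of 60–80% and overall improvement of 10–30%, the gain is 0.4–1.1 points if the odds of improvement in class III are twice those in class II, 2.0–4.3 points at four times, and 3.9–8.8 at eight times.

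**Checks for harm.**

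- A grid of 14,400 input combinations gave a smallest gain of 0.0.
- An OR of 1.3 in one class and 1.0 in the other, either way round, gave gains of 0.0 to 7.5 points.
- A separate simulation with region and LVEF in both models gave differences of −0.1 and −0.2 points where class mattered little or not at all, within Monte Carlo error. Under the null at 0.0248 it rejected 2.4% (current) and 1.9% (with class); 1000 runs, standard error about 0.5 points.

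**Effect on the odds ratio.** With a within-class OR of 1.20 and 70% class II, the current model targets 1.197 (15%/25%), 1.193 (15%/30%), 1.179 (10%/35%) or 1.165 (10%/45%).

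**The case against.** The case against is that there is no defect here, only a preference between two valid models.

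- The primary endpoint, CV death, total HF events, the renal composite and all-cause mortality are all analyzed with treatment and stratification factors only, so the NYHA model follows the plan's general convention. This is fair. But those outcomes are not defined against a baseline value, whereas KCCQ and NYHA are.
- The benefit rests on assumed rates. This stands: nothing in the documents supports a steep class gradient, and without one the gain is negligible.
- The larger gains come from the simpler calculation. This also stands. The SAP counts participants as not improved where "no measurement at Visit 6 is available due to stop of treatment prior to Visit 6", so some non-response is built in. With region, LVEF and the assumed non-response, the 8.6-point gain at OR 1.2 falls to 3.5.
- Changing a confirmatory model after SAP version 3.0 is not free, and the reported odds ratio shifts. True, and counted as a cost.
- A participant recorded as class I at baseline would fit neither level of a II vs III/IV factor. This is a coding point, met by grouping that person with class II.

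In the other direction, the early-stop branch tests at 0.0027/2, where a steep gradient matters more: at 10%/45%, OR 1.3 and N = 6000, power goes from 62.5% to 74.2%.

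**Conclusion.** The observation holds in both documents. The planned test is valid, so this is a suggestion to consider and not a correction. If the trial is not stopped early, the gain is nil to small in most scenarios. It reaches several points only if class III–IV participants improve several times as often as class II and the odds ratio is about 1.2 to 1.3. No scenario showed a loss beyond simulation error. Every class mix, improvement rate, odds ratio and non-response rate used here is an assumption, so the size of the gain in this trial cannot be established from the documents.

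**What to change.** Optional, and only before unblinding:

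1. Add baseline NYHA class as a two-level factor (II vs III/IV, the split already in SAP 4.5.6) to the primary logistic model in SAP 6.2.2.1. Pooling III with IV avoids a sparse class IV. Code any class I baseline with class II.
2. State that the odds ratio is then conditional on class as well as on region and LVEF, so its value differs from that of the current model.
3. Keep the current model as a sensitivity analysis.
4. Align protocol 9.4.1.2.

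If the model is left as it is, a sentence giving the reason would be enough.

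The cost is low. No new data are needed, and no further participants drop out of the analysis, since "Participants with missing baseline value will be excluded from the analysis" already applies. The change needs a SAP version after 3.0 and a protocol alignment. The SAP rests on a protocol amendment dated 26 OCT 2022 that is not among the documents supplied, so its wording on this endpoint should be checked first. The new model assumes a common odds ratio across II and III/IV, which the planned interaction test examines.
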